6 DATA HANDLING

6.1 Time points and Visit Windows

Day 1 is defined as the day of randomization visit. Relative days after Day 1 are calculated as (assessment date - Day 1 date) + 1. Relative days prior to Day 1 are calculated as (assessment date - Day 1 date). The day prior to Day 1 is Day -1.

All data will be analyzed using nominal study visits as defined in the Study Schedule and eCRF. No visit windows will be applied for summary and analysis.

In determining the baseline, if assessment on date of randomization is unavailable, then the last scheduled or unscheduled assessment before first study drug/randomization will be used instead.

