1. Informed consent must be obtained before any study-related procedures are conducted.

2. Idarubicin administered at a dose of 12 mg/m²/day by slow (10 to 30 minutes) IV injection/infusion daily on Days 1, 2, and 3.
3. Cytarabine administered at a dose of 100 mg/m²/day as a continuous 24-hour IV infusion on Days 1-7. Patients who do not achieve leukemia-free state (<5% bone marrow blasts) on bone marrow aspirate performed between Days 14-21 may receive a re-induction cycle with the same regimen ("7 + 3" ± CX-01). If in the Investigator's opinion, the patient is not fit to receive full re-induction cycle of "7 + 3" ± CX-01, at the Investigator's discretion the patient may receive "5 + 2" ± CX-01 which is 5 days of cytarabine (Days 1-5) and 2 days of idarubicin (Days 1 and 2).
4. CX-01 administered at a dose of 4 mg/kg as an initial bolus on Day 1 only, 30 minutes after completion of administration of the first dose of idarubicin.
5. CX-01 administered at a dose of 0.125 or 0.25 mg/kg/hour as a continuous 24-hour IV infusion on Days 1-7.
6. Height obtained at Screening only. Actual body weight will be measured at the beginning of each cycle to calculate treatment doses.
7. Hematology **must** include the following: hemoglobin, ANC, and platelets. All other hematology assessments should be performed only if standard of care and/or clinically indicated. Hematology samples will be collected daily until discharge and weekly thereafter until recovery.
8. Note: blood samples for PT/INR, aPTT and anti-Xa levels will be collected 12 hours after the bolus dose of CX-01.
9. Anti-Xa samples will be collected only on Days 1-8.
10. PT/aPTT will be collected daily on Days 1-8, and on Day 9, Day 11, and Day 13.
11. Chemistry (and comprehensive metabolic panel) includes BUN, serum creatinine, total bilirubin, ALT, AST, and alkaline phosphatase. Samples will be collected daily until discharge.
12. At selected sites, blood samples for steady-state PK analysis will be collected during the induction cycle from the first six randomized patients assigned to CX-01 on Days 3 and 5 at a single time point.
13. For females of childbearing potential only. All female patients will have a urine pregnancy test at Screening; positive urine tests must be confirmed by a serum pregnancy test.

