6.5.3 Randomization

Randomization will occur after eligibility is confirmed for consenting study participants. Study drug will be administered following randomization.

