7.6.5 Exploratory Analysis

Additional efficacy analyses will be performed as exploratory analysis for the following variables, summarized by treatment groups and analyzed in the same way as secondary analyses above.

- Duration of composite CR (if present)
- Days until neutrophil recovery to 2: 500/ LL (from date of randomization and from date of first study drug)
- Days until platelet recovery to 2: 20,000/ LL (from date of randomization and from date of first study drug)

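### SAP 6.1 sets no pre-dose condition on a randomization-date baseline, so coagulation change from baseline in the CX-01 arms can start from an on-drug value (minor)

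*SAP*

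**What the plan says.** SAP 6.1 states that "Day 1 is defined as the day of randomization visit". Its baseline sentence reads "In determining the baseline, if assessment on date of randomization is unavailable, then the last scheduled or unscheduled assessment before first study drug/randomization", and that value then serves instead. The randomization-date assessment is therefore the implied first choice, and it carries no condition that it precede dosing. The same section says "All data will be analyzed using nominal study visits as defined in the Study Schedule and eCRF", with no visit windows.

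Protocol Table 6-1 puts randomization, the CX-01 bolus, the start of the infusion and a coagulation draw all on Day 1. Footnote 8 gives the timing of the draw: "blood samples for PT/INR, aPTT and anti-Xa levels will be collected 12 hours after the bolus dose of CX-01". SAP Table 11-1 repeats that footnote. Footnotes 9 and 10 give the frequency: "Anti-Xa samples will be collected only on Days 1-8" and "PT/aPTT will be collected daily on Days 1-8, and on Day 9, Day 11, and Day 13". The other scheduled pre-treatment coagulation sample is at Screening, up to 28 days before randomization (Protocol 6.5.2).

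On the order of events, Protocol 6.5.3 says "Study drug will be administered following randomization". SAP 7.6.5 treats the two dates as separable, counting some recovery times "from date of randomization and from date of first study drug".

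**The concern.** A baseline should precede the treatment whose effect it is used to measure. Here a programmer who follows the rule can take a sample drawn during the CX-01 infusion. Control patients receive no bolus, so their baseline is never on CX-01 and the distortion differs by arm. Changes in the CX-01 arms are pulled toward zero. For PT and aPTT, the values after the infusion (Days 9, 11 and 13) could also appear as a fall below baseline. Anti-Xa sampling within the cycle stops at Day 8, so that second effect is not a concern there.

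Safety and tolerability is a primary objective (Protocol 5.1), and Protocol 6.8.10.1 singles out coagulation and bleeding for attention. The outputs that depend on this baseline are Table 14.3.2.2.3 (coagulation change from baseline) and Tables 14.3.2.2.12 and .15 (anti-Xa shift, counts and percentages). SAP 7.7.1 defines treatment-emergent events by date and time of first dose, so the SAP applies that precision elsewhere.

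**Working it through.** The plan gives no figure to reproduce. The check sets the baseline rule against the schedule and then sizes the result for aPTT.

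**1. Is the 12-hour sample on-drug?** The bolus is 4 mg/kg and the infusion rates are 0.125 and 0.25 mg/kg/hour (Protocol 6.4.1). Amount given by the draw = bolus + 12 h × rate:
- lower dose: 4 + 12 × 0.125 = 5.5 mg/kg
- higher dose: 4 + 12 × 0.25 = 7.0 mg/kg

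The infusion is still running, so the value is on-drug.

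**2. When does it count as the randomization-date assessment?** There are three readings:
- *Calendar date.* The draw falls on Day 1 only if the bolus is before 12:00. The bolus comes 30 minutes after a 10 to 30 minute idarubicin dose, so idarubicin must start before about 11:00 (12:00 - 30 - 30 min) to 11:20 (12:00 - 30 - 10 min). A later bolus pushes the draw past midnight, and the rule falls back to an earlier value, normally Screening.
- *Nominal Day 1 visit.* The scheduled Day 1 value is the 12-hour sample whatever the clock time.
- *Randomization on a date before dosing.* Any value on the randomization date is pre-dose, and there is no problem.

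The documents give no bolus clock times. Let f be the share of CX-01 patients with an on-drug baseline. Assuming evenly spread bolus times, f = 1 for 07:00 to 12:00, (12 - 8)/(16 - 8) = 0.5 for 08:00 to 16:00, and 0 for 12:00 to 20:00. The text therefore does not fix f.

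**3. Size for aPTT.** Inputs:
- The AML pilot used the same bolus and 6 mg/kg/day (Protocol Table 4-1). 6 / 24 = 0.25 mg/kg/hour, this trial's higher rate.
- Mean aPTT in the pilot was largely in the mid-30 s range (Protocol 6.4.4.1); 35 s is used here.
- No pre-dose mean is given. I assume 30 to 36 s; entry excludes values above 40 s.
- I assume aPTT at 12 hours resembles later infusion days. The bolus effect is stated to last less than 1 hour (Protocol 6.4.5.2).

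Lost shift per affected patient = on-infusion aPTT - pre-dose aPTT: 35 - 36 = -1 s to 35 - 30 = 5 s. A negative value means nothing is lost. The arm-mean loss is f times this range:

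| f (assumed) | Arm-mean lost shift at 35 s |
|---|---|
| 0 | 0 |
| 0.25 | -0.25 to 1.25 s |
| 0.5 | -0.5 to 2.5 s |
| 0.75 | -0.75 to 3.75 s |
| 1 | -1 to 5 s |

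At 40 s, the midpoint of the approximate 35 to 45 s range in Protocol 6.4.5.2, the per-patient loss would be 40 - 36 = 4 to 40 - 30 = 10 s. At 45 s it would be 9 to 15 s. However, 45 s is the level above which CX-01 is interrupted (Protocol 6.4.4.2), so it is a ceiling and not an expected mean. The documents report no aPTT for the lower rate in AML and nothing from which to size PT/INR or anti-Xa.

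**The case against.** The strongest reply has four parts.

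- **Intent.** The fallback wording shows that a pre-dose baseline was meant. Probably so, but the condition is not attached to the first-choice value, and nothing else in either document supplies it.
- **Date rule.** The baseline sentence selects by date and admits unscheduled samples, so the nominal-visit sentence may govern only by-visit summaries. This stands. A reader might infer that all CX-01 patients, 75 × 2/3 = 50 of the planned 75, would have an on-drug baseline. That needs the nominal-visit reading, and the documents do not establish it. The eCRF, which SAP 6.1 also relies on, is not available here.
- **Visibility.** A reader might also infer that a CX-01 effect on coagulation would be hidden. It would not. The shell for Table 14.3.2.2.3 prints the Baseline row and each visit's absolute values by arm beside the change, and the anti-Xa shift tables show baseline category by arm. The over-time figures and the worst-to-last-grade tables do not use this baseline. Change is attenuated, but the on-drug levels stay visible.
- **Size.** Protocol 6.4.4.1 cites 31.5 to 36 s, labelled a therapeutic range and so an imperfect stand-in for pre-dose values. With it, the loss at 35 s is 35 - 36 = -1 to 35 - 31.5 = 3.5 s. That is fair, and it fits a minor rating.

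Footnote 8 is also loosely scoped, since it sits on a row that includes Screening. It remains the only timing given for the Day 1 draw. If a site also takes an unscheduled pre-dose Day 1 sample, no rule says which value is baseline.

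**Conclusion.** The gap is real and minor. As written, SAP 6.1 permits an on-drug coagulation baseline in the CX-01 arms and never in control, which attenuates the changes in Table 14.3.2.2.3 and the shifts in Tables 14.3.2.2.12 and .15. The number of patients affected cannot be determined from the documents and could be none, for example if randomization precedes the dosing date. For affected patients at the higher rate, the mean aPTT shift lost is about -1 to 5 s. This rests on an on-infusion mean of 35 s, an assumed pre-dose mean of 30 to 36 s, and 12-hour values resembling later infusion days. Fibrinogen and D-dimer have no Day 1 draw and are unaffected. The safety analysis is descriptive, and no test or endpoint changes.

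**What to change.** In SAP 6.1:

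1. Define laboratory baseline as the last non-missing assessment before the first study treatment, using date and time where recorded.
2. State that the scheduled 12-hour Day 1 PT/INR, aPTT and anti-Xa sample in the CX-01 arms is post-baseline. The coagulation baseline is then a sample documented as pre-dose, or otherwise Screening. Apply the same coagulation rule in the control arm for comparability.
3. State the scope. The rule in 6.1 is global, and hematology and chemistry also have Day 1 draws. Either apply the new definition to all laboratory change-from-baseline and baseline shift tables (14.3.2.2.2 to .4 and .11 to .16), or limit it expressly to coagulation (.3, .12 and .15).

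The cost is a few sentences plus reprogramming of three tables if limited to coagulation, or 3 + 6 = 9 if applied throughout. No new samples are needed: Screening coagulation is already collected, and Protocol 6.4.6 already has dosing date and time recorded. The coagulation listing shell (16.2.24) shows a collection date but no time, so many patients may default to a Screening value that can be up to 28 days old. That is the main downside.

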6.2 Handling of Dropouts or Missing Data (where applicable)

For ITT analysis, patients with partial or missing data to determine morphologic complete remission on the eCRF form will be considered as not having met the criteria morphologic complete remission. For PP analysis and elsewhere, only the complete cases will be analyzed and no missing value imputation will be carried out.

Incomplete AE-related dates will be handled as follows:

- In cases where:
 - o the onset date is completely missing or
 - o the onset is in the same year (only the onset year is available) as the start of study treatment or
 - o the onset is in the same month and year (only the day is missing) as the start of study treatment or
 - o either the onset day or month is missing but the year is not before start of study treatment then the onset date will be replaced by the minimum of start of study treatment and AE resolution date.
- In all other cases the missing onset day or onset month will be replaced by first day or January.

Statistical Analysis Plan

Version: Final

Date of Issue: 20 March 2018

Cantcx Pharmaceuticals, Inc. Protocol No. CNTX-CX-01 2015 AML I Covance Study ID: 000000146201

- Incomplete stopping dates will be replaced by the last day of the month (if the day is missing only), unless this will result in a date after the date of death. If the imputed date will exceed the date of death, the date of death will be used as the stopping date. No imputation is needed if the event is ongoing.
- In all other cases the incomplete stopping date will not be imputed.

To impute missing day of follow-up dates (such as safety long term follow up) or Disease History, the missing day will be taken as the 15th of the month, as long as month and year is available. In all other cases missing or incomplete dates will not be imputed.

In patient listings, the documented date from cCRF will be reported (e.g. .May2016 in case where the day is missing, but month and year are available).

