10. APPENDICES

APPENDIX A – Acute Myeloid Leukemia Response Criteria

The IWG consensus criteria for treatment response in AML will be used to evaluate response to treatment.

Definitions of Remission

Morphologic complete remission (CR): ANC >1000/ μ L, platelet count >100,000/ μ L, <5% bone marrow blasts, no Auer rods, no evidence of extramedullary disease.

Morphologic CR with incomplete blood count recovery (CRi): CRi, which is CR without recovery of neutrophils and/or platelets (ANC may be <1000 μ L and/or platelet count <100,000/ μ L).

Partial remission (PR): ANC >1000/ μ L, platelet count >100,000/ μ L and at least a 50% decrease in the percentage of marrow aspirate blasts to 5 to 25%, or marrow blasts <5% with persistent Auer rods.

Progressive Disease

Progressive disease (PD) is defined as any one of the following:

- More than 50% increase in bone marrow blast % from best assessment (with a minimum threshold of 20% blasts in the marrow).
- >50% increase in circulating malignant blasts (with absolute blasts >1000/ μ L).
- Development of biopsy-proven extramedullary leukemia (if the patient has extramedullary disease at baseline then PD will be defined by blood and marrow criteria or if new sites of extramedullary disease appear).

In patients who present with initial marrow blast percentage sufficiently high to preclude the ability to base disease progression on a >50% increase in marrow blast percentage; disease progression should be based on peripheral blood criteria or development of extramedullary leukemia.

Stable Disease

Patients who fail to achieve CR, CRi or PR and who do not have criteria for PD will be defined as having stable disease. If the patient dies prior to response assessment at the end of Cycle 1, then they will be classified as “Indeterminate”.

Relapse from CR or CRi

Reappearance of leukemia blasts in the peripheral blood; or >5% blasts in the bone marrow not attributable to another cause (e.g., recovery of normal cells following chemotherapy-induced aphasia); or appearance or reappearance of extramedullary disease and the bone marrow blast percentage is >5% but < or equal to 20%, than a repeat bone marrow performed at least 7 days after the first marrow examination and documenting bone marrow blast percentage is >5% is necessary to establish relapse.

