2.6 Sample Size and Power

A total of 25 evaluable patients per arm will provide 71.8% power for each test comparing a dose with control via a Fisher's exact test at I-sided alpha = 0.15 to detect a difference between a control proportion 0.55 and an experimental dose proportion 0.80; these tests will be conducted in a fixed sequence: higher dose versus control first and lower dose versus control second, with the second test considered exploratory (failed) if the first test fails.

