5 ANALYSIS POPULATIONS

The analysis sets that will be used for statistical analyses are as follows:

Intent-To-Treat (ITT): This includes all randomized patients. Patients will be analyzed according to the treatment to which they are randomized. The ITT Population will be the primary analysis set for the efficacy variables.

modified-Intent-To-Treat (mITT): This includes all randomized patients who received at least one dosage of study drug. Patients will be analyzed according to the treatment to which they are randomized.

Per Protocol (PP): Supporting analyses will be conducted on the PP Population, comprising all patients randomized and treated without major protocol deviations during the trial. This population will be documented before final database lock. PP Population will be analyzed according to the treatment to which they received.

The following are considered protocol deviations for the purpose of identifying the per protocol set:

1. Patients who were subsequently found to be not complying with the inclusion and exclusion criteria
2. Patients who are not compliant with study restrictions (eg. use of prohibited medication (generic drug name) or prohibited treatment therapy)
3. Patients who continued in study but should have been withdrawn according to withdrawal criteria
4. Patients who are not compliant with study drug treatment dose modification or stoppage rules (either temporary or permanent).
5. Patients who took incorrect study drug (CX-01 or other) dose, frequency, timing or method of drug delivery (e.g. subject overdosed with study drug, incomplete study drug administered).

6. Patients who took different study drug than the study drug to which they were randomized.
7. Patients who do not have post baseline data anywhere in the system.

Items 1 to 5 are routinely monitored in the study as part of the study monitoring plan.

Safety: All patients who received at least one dose of study treatment. Patients will be included in the analyses according to the treatment they received. The Safety Population will be used in the analyses of all safety endpoints.

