7 STATISTICAL METHODS

7.1 General Principles

All data processing, summarization and analyses will be performed using the Hosted SAS Environment Version 9.3 (or later) of the SAS[®] statistical software package.

Unless specified otherwise, data will be displayed using the following treatment group labels, in the order presented:

- Control,
 - those who are on Idarubicin + Cytarabine therapy only
- Low CX-01,
 - those who are on Idarubicin + Cytarabine + plus lower dose CX-01
- High CX-01,
 - those who are on Idarubicin + Cytarabine + plus higher dose CX-01
- Overall

All data collected will be presented in listings by treatment group, site, subject and visit (where applicable), unless otherwise specified.

Data will be presented in summary tables by treatment group, and visit (where applicable). The category "Missing" will be presented if the number missing is greater than zero for at least one treatment group.

Descriptive summary statistics for continuous variables will include the number of subjects (N), mean, standard deviation (SD), median and range.

Statistical Analysis Plan

Version: Final

Date of Issue: 20 March 2018

Cantex Pharmaceuticals, Inc. Protocol No. CNTX-CX-01 2015 AML I Covance Study ID: 000000146201

Descriptive summary statistics for categorical variables (such as gender, race) will include frequency counts and percentages [n (%)]. Unless stated otherwise in the table shells, the denominator for percentage calculations for a particular variable will be the number of subjects with non-missing data.

Dates will be displayed as DDMMYYYY.

All significance tests will be two-sided and use a 5% significance level except for primary outcome, which is tested at I -sided at 15% level of significance.

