7.6.2 Secondary Efficacy Analysis

The primary efficacy analysis will be repeated using the PP Population as a supportive analysis along with CRi and composite CR for ITT and PP. Complete response rates and composite complete response rates and confidence intervals will also be reported for key subgroups (De-novo vs secondary AML at diagnosis, Age < 70 vs Age ≥ 70, ECOG performance status = 1 vs ECOG performance status = 2). The following secondary analyses will be performed on the ITT population. Analyses of EFS, LFS, time to neutrophil and platelet recovery, and OS will be descriptive. Kaplan-Meier (KM) estimates will be used to estimate the survival distribution for each arm and KM plots will be produced to accompany these analyses. 95% Confidence Intervals will be reported for medians and KM estimates. Duration of response will be analyzed using a similar approach; the survival distributions will be estimated as cumulative incidence functions.

Statistical Analysis Plan

Version: Final

Date of Issue: 20 March 2018

Cantcx Pharmaceuticals, Inc. Protocol No. CNTX-CX-01 2015 AML I Covance Study ID: 0000014620 I

Mortality rate at Day 30, Day 60, and Day 90 will be reported using descriptive statistics in a manner similar to the reporting of the morphologic CR rate. The time to neutrophil and platelet recoveries will be reported using the following descriptive statistics: N, mean, SD, median, minimum, maximum, and the 1st and 3rd quartiles.

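### Missing response counts as failure only for ITT morphologic CR; PP CR is complete-case, and CRi, composite CR and mITT response rates are complete-case or have no rule

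*SAP*

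**What the plan says.** SAP section 6.2 has two rules. The first is confined to morphologic CR in ITT: "patients with partial or missing data to determine morphologic complete remission on the eCRF form will be considered as not having met the criteria". The second reads: "For PP analysis and elsewhere, only the complete cases will be analyzed and no missing value imputation will be carried out". Section 7.1 adds a default for percentages: unless the table shells differ, "the denominator for percentage calculations for a particular variable will be the number of subjects with non-missing data".

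The analyses outside the first rule are set out in section 7.6.2: "The primary efficacy analysis will be repeated using the PP Population as a supportive analysis along with CRi and composite CR for ITT and PP". The shells add mITT tables for CR, CRi and composite CR (Tables 14.2.2, 14.2.5 and 14.2.8). The legible footnotes of the CR shells give the interval and test methods but no denominator; the overall-survival shell does state its denominator. Section 7.6.3 plans no sensitivity analysis.

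On early death, Protocol Appendix A says: "If the patient dies prior to response assessment at the end of Cycle 1, then they will be classified as" Indeterminate. The bone-marrow shell lists both Indeterminate and Unknown as response values. The SAP maps neither to failure or to missing.

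Two entries in the PP deviation list (SAP section 5) also matter. Item 7 is "Patients who do not have post baseline data anywhere in the system". Item 5 concerns incorrect dosing and gives "incomplete study drug administered" as one example.

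**The concern.** In a complete-case response rate, an unassessed patient leaves both numerator and denominator. If most such patients are non-responders, the arm that loses more of them shows a higher rate with no true benefit. SAP section 3.1 makes this plausible for early deaths: CR counts only if documented on or after day 21 from randomization, so a patient who dies before then cannot have a qualifying response.

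Imbalance between arms is possible but not documented. The trial is open-label, and Protocol section 6.4.4.2 has hold and stop rules for CX-01 that the control arm cannot trigger. Those rules bear on who might be called a PP deviation. Missing response is a separate mechanism.

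The PP and composite CR analyses are there to support the primary result, and no sensitivity analysis is planned. If their direction depends on who happened to be assessed, they cannot corroborate it.

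**Working it through.** **Inputs.** SAP sections 2.6 and 7.6.1 give 25 evaluable patients per arm, control CR 0.55, experimental CR 0.80, and Fisher's exact test, one-sided at 0.15. The missing-response rates are assumptions, because the documents give none.

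**Step 1: reproduce the plan's figure.** The SAP states: "A total of 25 evaluable patients per arm will provide 71.8% power for each test comparing a dose with control via a Fisher's exact test". With i control and j CX-01 responders, the p-value is P(H ≥ j), where H is hypergeometric (50 patients, i + j responders, 25 on CX-01). The rejection probability is

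Σᵢ Σⱼ Bin(i; 25, p_C) · Bin(j; 25, p_T) · 1[p-value ≤ 0.15].

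- p_C = 0.55, p_T = 0.80: 71.7%, against 71.8% stated. The normal approximation gives 81.1%, so the stated figure is the exact one.
- p_C = p_T = 0.55: 10.0%. This is the actual false-positive rate, below the nominal 15% because the test is discrete.

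**Step 2: shift in the apparent rate.** If a share m of an arm is unassessed and all of these are non-responders, the expected complete-case rate is p/(1 − m). At p = 0.55:

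- m = 5%: 0.55/0.95 = 57.9%
- m = 10%: 0.55/0.90 = 61.1%
- m = 15%: 0.55/0.85 = 64.7%
- m = 20%: 0.55/0.80 = 68.8%

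**Step 3: false-positive rate.** Each patient is a responder (probability 0.55), missing (m) or an observed non-responder (0.45 − m). Fisher's test is applied to assessed patients only, by exact enumeration.

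| Missing, control / CX-01 | False-positive rate |
|---|---|
| none | 10.0% |
| 5% / 5% | 9.2% |
| 10% / 10% | 9.2% |
| 20% / 20% | 8.5% |
| 5% / 10% | 13.5% |
| 5% / 15% | 19.4% |
| 10% / 20% | 20.2% |
| 20% / 10% | 3.1% |

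Doubling the actual 10.0% takes about 10 to 12 points more missingness on CX-01, or 2.5 to 3 patients of 25. Doubling the nominal 15% takes about 15 to 18 points.

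**Step 4: how far this depends on the assumptions.** At 10/20%, simulation (200,000 runs) gives 14.4% if 75% of missing patients are non-responders, and 9.1% if missingness is unrelated to response. For composite CR at an assumed true rate of 65%, the one-sided rate is 9.2% with none missing and 23.9% at 10/20%. If a two-sided 5% test applies, the total rate at true CR 55% goes from 3.2% to 5.4% at 10/20%; the part favouring CX-01 goes from 1.6% to 5.0%.

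**Step 5: after the change.** If missing patients are true non-responders and are counted so, the false-positive rate is 10.0% whatever the missing rates, and power stays at 71.7%.

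**The case against.** Four stronger readings are tempting, and the documents do not support them.

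- **That early deaths are dropped.** Appendix A gives them a recorded class, so they are not plainly missing. What stands is that the SAP does not say how that class is counted.
- **That PP excludes early deaths and toxicity stops.** Item 7 needs no post-baseline data at all, whereas the schedule has daily laboratory tests on Days 1 to 7, so a treated patient who died early would normally have some. Item 4 concerns failure to follow the stopping rules; a stop made under them is compliance. Section 7.5 counts expected days only up to withdrawal. Item 5 is loosely worded and needs clarifying, but does not state such an exclusion.
- **That complete-case handling of ITT CRi and composite CR, and of mITT, is a stated fact.** 'Elsewhere' may mean other endpoints or other populations. For ITT CRi and composite CR, the second reading leaves no rule. The composite CR definition in section 3.2 does not help: it covers patients who respond and then fail between days 21 and 42, not those never assessed.
- **That the false-positive rate doubles.** Equal missingness gives no inflation, and excess missingness on control makes the test conservative.

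The test itself is also unsettled for CRi and composite CR. Section 7.6.2 can be read as repeating the one-sided 15% test, while section 7.1 sets two-sided 5% for everything but the primary outcome, and the shells for Tables 14.2.4 to 14.2.9 delete the one-sided footnote. The one-sided figures therefore apply most directly to PP CR.

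Finally, the consequence is limited. The ITT primary test already counts missing as failure, so the fixed sequence is untouched, and the trial is described as exploratory.

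**Conclusion.** The gap is real, in narrowed form. PP CR is complete-case by direct statement; CRi and composite CR in ITT, and all mITT response rates, are complete-case or undefined; Indeterminate and Unknown are unmapped. The bias favours CX-01 only if unassessed patients are mostly non-responders and are more frequent on CX-01. At 25 per arm, and with every missing patient a non-responder, an excess of 5 points raises the false-positive rate from 10.0% to 13.5%, still under the nominal 15%. An excess of 10 points takes it to 19.4% (5/15%) or 20.2% (10/20%). These are conditional illustrations, not forecasts. Only supportive and secondary analyses are affected.

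**What to change.** In SAP section 6.2, state that patients with missing, Indeterminate or Unknown response, including those who die before assessment, count as non-responders for CR, CRi and composite CR in ITT, mITT and PP, with all patients in that population as the denominator. Give complete-case results only as a sensitivity analysis, and replace the empty entry in section 7.6.3 accordingly. In section 5 item 5, clarify that death, or a drug stop made in line with the protocol's own rules, is not by itself a deviation that excludes a patient from PP. State also which level and sidedness apply to PP CR, CRi and composite CR.

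The cost is SAP wording and slightly lower response rates in supportive tables. The non-responder rule has its own bias if missingness is unrelated to response: at 10/20% missing and true CR 55% in both arms, the reported rates would be 0.55 × 0.90 = 49.5% and 0.55 × 0.80 = 44.0%. That is why the complete-case result should be kept beside it. Data collection and the primary test do not change.
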